PROTOCOL

Internet-based intervention versus face-to-face clinical care for tinnitus: A randomized control trial

Clinical Trials registration number: NCT02665975

Principle Investigator: [name] ([contact])

Ethical approval: Cambridge South Research Ethics Committee, 16/EE/0148. HRA approval under IRAS project identification number 195565

Sponsor: Anglia Ruskin University

Grant: British Society of Audiology Applied Research Grant Fund

Clinical Sites: Norfolk and Norwich University Hospitals NHS Foundation Trust

Hinchingbrooke Health Care HNS Trust

Milton Keynes University Hospital NHS Foundation Trust

Date of protocol version: 10 July 2016

INTRODUCTION

Tinnitus places a burden on healthcare systems, leaving many people with distressing tinnitus without appropriated care. Innovative management strategies are required to improve access to evidence-based treatments. A guided Internet-based intervention for tinnitus was therefore developed (iCBT) for a UK population. Initial clinical trials indicated that iCBT in the UK is effective at reducing tinnitus distress and associated comorbidities. The aim of this randomized control trial is to compare this iCBT intervention to that of standard tinnitus care provided face-to-face in clinical settings, for reducing tinnitus distress and associated problems.

OBJECTIVES

The primary aim of this study is to evaluate the effectiveness of iCBT for tinnitus distress, compared to standard care. The key secondary objective is to determine the effectiveness of iCBT for tinnitus related comorbidities, compared to standard care. Further objectives are to determine the longer-term effects of iCBT compared to that of standard care, two months post-intervention and establish if there are any predictor variables associated with outcomes for iCBT compared to those for standard care.

STUDY DESIGN

A randomised, multi-centre, two-arm parallel group, non-inferiority trial with a sequential adaptive design and a two-month follow-up will be followed. The experimental group will receive eight weeks of guided internet-delivered treatment

(iCBT) as seen in Figure 1. The control group will receive a standard individual face-to-face audiological care. The hypothesis is that there will be no difference in outcomes for the treatment and control groups. These groups will be followed prospectively for two months, to establish the maintenance and effectiveness of both treatments on tinnitus distress.

[figure not shown]

Figure 1: Trial design

PARTICIPANTS

Sample size

Sample size calculations have indicated that 65 participants are required per group. Estimated recruitment is 50 participants from both Norfolk and Norwich University Hospital and Hinchingsbrookes Hospital and 30 from Milton Keynes University Hospital.

ENROLLMENT

All adult patients referred to the three participating Tinnitus Clinics during the recruitment period, who meet inclusion criteria, will be invited to participate. It is estimated that recruitment will occur over a two-month period. Eligibility is determined on the basis of the following criteria:

Inclusion Criteria

- i) Having undergone a clinical evaluation by either their ENT Specialist or the Audiologist at participating sites, to rule out the presence of serious auditory pathology
- ii) Experiencing tinnitus distress deemed to require a referral to the tinnitus clinic by the referring ENT Specialist or Audiologist
- iii) Aged 18 years and over, living in the UK with the ability to read and type in English
- iv) Regular access to a computer and the internet and the ability to use these

Exclusion Criteria

- i) Reporting any major medical or psychiatric conditions
- ii) Undergoing any tinnitus therapy concurrently to partaking in this study

Withdrawal

Participants will be informed of the right to withdraw without penalty. Statistical analysis will be done on an intention to treat basis unless they request all data removal.

SCHEDULE

Recruitment will be aimed to start in August, with initial participants from the face-to-face interventions to be seen between September 2016-January 2017 for their initial and follow-up appointments. Study close out will be two months after their intervention ended, which is estimated to be by April 2017. A broad outline of responsibilities is given in Table 1.

Table 1: Responsibilities of clinical sites and PI

Recruitment and distributing PIS	Clinical sites
Providing information about the study	Principle investigator (PI)
Study consent	Online (PI)
Assessment	Online. PI to pass on results to clinical sites
Initial telephonic contact with participants	PI
Randomisation and allocation	PI and PI to pass on allocation to clinical sites
Triage for the need for amplification	Clinical sites. Appointments to be considered on an individual basis

iCBT group: 8 weeks treatment	PI
Face to face standard care group treatment and appointment worksheet completion	Clinical sites
Post-intervention outcome measures	Online. PI to pass on results to clinical sites
Post treatment phone call	PI
Follow up assessment	Online. PI to pass on results to clinical sites

Data management

All personal data will be kept confidentiality. Each participant will be assigned a random user code (four digits followed by four letters), this is used by therapists to identify the participant during treatment. Secure communications to take place between clinicians and the therapist via the tackling tinnitus website, for which login details have been provided. All personal participant information to be saved safely according clinical sites IT policies.

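### Does the label 'sequential adaptive' conflict with the recruitment calendar and with the principal investigator's roles in Table 1?

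*Combined protocol and SAP*

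**What the plan says.** All references are to the combined protocol and SAP.

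- **Study Design.** A "non-inferiority trial with a sequential adaptive design and a two-month follow-up will be followed". On treatment length: "The experimental group will receive eight weeks of guided internet-delivered treatment". The readable text does not say what is adapted, when or by whom. Figure 1, captioned as the trial design, is not reproduced in the text available, so what it adds cannot be judged.
- **Sample size.** "Sample size calculations have indicated that 65 participants are required per group". The expected contributions of the three sites are 50, 50 and 30.
- **Enrollment.** "It is estimated that recruitment will occur over a two-month period".
- **Schedule.** Recruitment is aimed to begin in August, with "initial participants from the face-to-face interventions to be seen between September 2016-January 2017 for their initial and follow-up appointments". Close-out comes two months after treatment ends, estimated as April 2017.
- **Table 1.** Randomisation and allocation: "PI and PI to pass on allocation to clinical sites". The row "iCBT group: 8 weeks treatment" is also assigned to the principal investigator, and face-to-face care is assigned to the sites. Post-intervention measures: "Online. PI to pass on results to clinical sites". The follow-up row reads the same, and neither row is split by arm. The Schedule section presents the table only as a rough summary of who does what.

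**The concern.** A sequential design normally acts on accumulating outcomes while there is still something to decide. Here recruitment is planned to last hardly longer than one course of iCBT, so almost everyone would be enrolled before the first outcome arrived. On that reading the trial carries the name of a design that its own dates defeat.

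If recruitment ran late, outcome-driven decisions would become possible, but a second difficulty would appear. The person through whom outcomes pass would still be allocating patients, and that person also delivers one of the two treatments. In a non-inferiority trial, a decision to stop or extend made with knowledge of results by arm could bias the conclusion. An unadjusted extra look would also raise the chance of a false claim of non-inferiority.

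**Working it through.** **1. The plan's own figure.** 50 + 50 + 30 = 130 = 2 × 65, so the site estimates agree with the target. The 65 itself cannot be rebuilt, because alpha, power, margin and standard deviation are not given. Nothing below depends on it.

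**2. The planned calendar.** Take two months as 61 days, eight weeks as 56 days, and treatment starting on the day of enrolment. This is the case most favourable to an early look.

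| Recruitment opens | First iCBT completion (+56 days) | Recruitment ends (61 days) | Overlap, inclusive |
|---|---|---|---|
| 1 Aug 2016 | 26 Sep | 30 Sep | 5 days |
| 15 Aug 2016 | 10 Oct | 14 Oct | 5 days |
| 31 Aug 2016 | 26 Oct | 30 Oct | 5 days |

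Only people enrolled in the first 5 days can have an outcome before enrolment closes, and only those due in the last 5 days can be spared. The accrual shapes are assumed.

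| Accrual | First 5 days: share, of 130 | Last 5 days: share, of 130 |
|---|---|---|
| Even (5/61) | 8.2%, 10.7 | 8.2%, 10.7 |
| Front-loaded, Beta(1,3) | 22.6%, 29.4 | 0.1%, 0.1 |
| Back-loaded, Beta(2,1) | 0.7%, 0.9 | 15.7%, 20.4 |

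With even accrual, about 65 × 8.2% = 5.3 of the early outcomes would be from the iCBT arm. A one-week gap between enrolment and treatment removes the overlap: 61 − 56 − 7 = −2 days.

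**3. Timing of a look.** With even accrual, a fraction f of post-treatment outcomes is in hand on day 56 + 61f. That is day 62.1 for 10%, 71.3 for 25% and 86.5 for 50%. All fall after day 61, so none spares anyone. The first two-month follow-up outcome arrives about day 56 + 61 = 117.

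**4. If recruitment overran** (lengths T assumed, 56 days applied to both arms). Outcomes in hand when enrolment ends are 130 × (T − 56)/T:

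- T = 92: 50.9
- T = 122: 70.3
- T = 184: 90.4

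A look at half the outcomes falls on day T/2 + 56, which precedes T only if T > 112. It leaves 130 × 5/122 = 5.3 people unallocated at T = 122, and 130 × 36/184 = 25.4 at T = 184.

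These counts are fragile, because no duration is stated for face-to-face care. If control outcomes took 84 days (assumed), the half-outcome look moves to T/2 + 70. It then leaves nobody at T = 122 and 130 × 22/184 = 15.5 at T = 184.

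**5. Error rate, for illustration only.** Suppose an unadjusted test at n1 is followed, if it fails, by another at n2. The overall error is 1 − Φ₂(z, z; ρ) with ρ = √(n1/n2).

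| n2 | ρ | One-sided alpha 2.5% (assumed) | One-sided alpha 5% (assumed) |
|---|---|---|---|
| 1.5 × n1 | 0.816 | 3.85% | 7.42% |
| 2 × n1 | 0.707 | 4.16% | 8.01% |

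The plan states no alpha, no such look and no such extension.

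**6. The passages side by side.** The label does not say what is adapted. The calendar shows only that looks meant to cut enrolment short would achieve almost nothing. A look after enrolment closes could still lead to an extension or a new sample size, which is the situation priced in step 5. Allocation that adapts to baseline factors would need no outcomes at all. Table 1 conflicts with no other sentence, since the readable text promises neither blinding of the principal investigator nor separation of roles.

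**The case for a change.** The strongest case for a change is that the 5-day gap uses only the plan's own durations, and that every reading of the label leads to trouble. If it means stopping enrolment early, the dates defeat it. If it means extension or re-sizing, the decision falls to someone who receives the outcomes and treats one arm, with no boundary and no independent party named. Deleting the phrase costs a few words.

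Much of this stands. The arithmetic is right, the term is undefined in the readable text, and the overlap of roles has no stated protection. Three parts do not carry through.

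- The charge that the trial cannot be what it is called assumes one meaning of the label. The extension reading shows that another meaning remains feasible.
- Biased allocation needs discretion over, or foreknowledge of, the next assignment. The text does not say whether the list is prepared in advance or concealed, so bias is possible but not shown.
- Neither remedy answers the worry about roles. If the phrase is deleted, the principal investigator still allocates with outcomes in hand. If a look plan with an independent statistician is written, staff are added, yet individual results still pass through the principal investigator, who knows each allocation and could assemble results by arm.

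**Conclusion.** No change to the plan is needed. What remains is an undefined label, a gap that an analyst fills sensibly. With 65 per group fixed and no look, boundary or adaptation described, the natural course is to recruit to target and analyse the completed sample. Run that way, the trial gives the same result whether or not the phrase is present.

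The calendar point is correct but small. At most about 11 of 130 people could be spared with even accrual, at a look with about 11 outcomes, and none could be spared once treatment starts a week or more after enrolment. This rests on 61-day recruitment and 56-day treatment; the overrun counts also rest on assumed lengths and on a control-arm duration that the plan does not give. The error rates of 3.85% to 8.01% describe a procedure that the plan does not propose and are not a defect of it. The overlap of roles in Table 1 is a separate matter from the label and is not shown to cause bias.

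This conclusion assumes that Figure 1 does not set out outcome-driven looks. If it does, their timing and error control would have to be judged from it.

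### The trial is declared non-inferiority, but its only hypothesis is no difference and it gives no margin or decision rule, so no test that could establish non-inferiority is prespecified.

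*Combined protocol and SAP*

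**What the plan says.** The Study Design section describes the trial as follows: "A randomised, multi-centre, two-arm parallel group, non-inferiority trial with a sequential adaptive design and a two-month follow-up will be followed". Later in the same paragraph comes the only hypothesis in the document: "The hypothesis is that there will be no difference in outcomes for the treatment and control groups".

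The Objectives section puts the primary aim in terms of effectiveness and does not mention non-inferiority: "The primary aim of this study is to evaluate the effectiveness of iCBT for tinnitus distress, compared to standard care". No instrument for tinnitus distress is named.

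The primary time point is not labelled, but it can be inferred to be the end of treatment. The two-month comparison is placed lower in the hierarchy ("Further objectives are to determine the longer-term effects of iCBT compared to that of standard care, two months post-intervention"), and Table 1 lists "Post-intervention outcome measures" separately from the follow-up assessment.

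The Sample size section says "Sample size calculations have indicated that 65 participants are required per group" and gives none of the inputs. The one statement about analysis is under Withdrawal: "Statistical analysis will be done on an intention to treat basis unless they request all data removal". There is no statistical analysis section.

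**The concern.** A non-inferiority trial succeeds by rejecting the hypothesis that the new treatment is worse than the comparator by at least a stated margin. That requires a margin, an error level and a rule linking the confidence interval to the margin. None of these appears. The hypothesis that does appear cannot do the job: if it is a null hypothesis, failing to reject it is not evidence that iCBT is acceptably close to standard care, and a smaller or noisier trial would fail to reject it more often.

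This affects the primary comparison of an internet treatment with existing face-to-face care. The protocol does not say that a non-significant result counts as success, but nothing in it rules that reading out. Nor does anything in it prevent a margin being chosen once the results are known.

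**Working it through.** **Can 65 per group be reproduced?** No. The document gives no margin, SD, alpha, sidedness, power or dropout allowance. The only available check is arithmetic: 2 × 65 = 130, which agrees with the site estimates of 50 + 50 + 30 = 130 if 50 is meant for each of the first two hospitals. The remaining steps ask what 65 per group is compatible with.

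**Assumptions (not in the document).** Outcome in SD units, higher = worse; equal SDs; 1:1 allocation; 65 evaluable per arm; one final analysis with no interim looks.

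**Step 1. Standard error.** SE = √(2/65) = 0.1754 SD. Degrees of freedom are 2 × 65 − 2 = 128, and the two-sided 5% critical t is 1.9787.

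**Step 2. Non-inferiority margins that 65 per group fits.** With true difference 0, margin = (z for one-sided alpha + z for power) × SE:

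| One-sided alpha | Power | Margin (SD) |
|---|---|---|
| 5% | 80% | (1.645 + 0.842) × 0.1754 = 0.436 |
| 2.5% | 80% | (1.960 + 0.842) × 0.1754 = 0.491 |
| 5% | 90% | (1.645 + 1.282) × 0.1754 = 0.513 |
| 2.5% | 90% | (1.960 + 1.282) × 0.1754 = 0.569 |

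**Step 3. Superiority effects that 65 per group fits.** For a two-sided 5% t-test, the detectable difference is 0.495 SD at 80% power and 0.573 SD at 90%. These almost coincide with the one-sided 2.5% margins in Step 2, so the sample size does not show which kind of test was planned.

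**Step 4. What follows if non-significance is read as success.** From the noncentral t distribution with noncentrality d/SE:

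- iCBT truly 0.3 SD worse: probability of a non-significant result 0.603.
- iCBT truly 0.5 SD worse: 0.192.

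**Step 5. What a non-significant result can hide.** The largest non-significant observed deficit is 1.9787 × 0.1754 = 0.347 SD. At an observed deficit of 0.34 SD, just inside that limit, the 95% interval is 0.34 ± 0.347, or −0.007 to 0.687 SD. The upper limit exceeds every margin in Step 2. The one-sided 5% margins (0.436 and 0.513) pair strictly with a 90% interval, whose upper limit is 0.34 + 0.291 = 0.631; the conclusion is the same.

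**Step 6. Why the unstated margin matters.** Power at 65 per group, one-sided 2.5%, true difference 0, is Φ(margin/SE − 1.960):

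| Margin (SD) | Power |
|---|---|
| 0.2 | 20.6% |
| 0.3 | 40.1% |
| 0.4 | 62.6% |
| 0.5 | 81.3% |

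**Step 7. Sensitivity to dropout.** If 65 already includes an allowance, assumed here to be 20%, then 65 × 0.8 = 52 are evaluable and SE = √(2/52) = 0.1961. The margins, in the order of Step 2, become 0.488, 0.549, 0.574 and 0.636 SD. The non-significant rates in Step 4 become 0.671 and 0.286.

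**The case against.** **The hypothesis sentence may be informal.** It may state the expected true effect, and a true difference of zero is a normal planning assumption for non-inferiority; Step 2 uses it. This is a fair reading and softens the charge of contradiction. It does not fill the gap, because no margin-based hypothesis or criterion appears anywhere else.

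**A margin may exist elsewhere.** The protocol is short and refers to a sample-size calculation that it does not show. That is possible, and the finding is limited to this document. The missing figure is captioned as the trial design and is cited in the text only for the iCBT arm, and nothing at this point looks redacted. If a margin was fixed, recording it here is simple.

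**The 60% and 19% figures assume a rule the protocol does not contain.** Correct. They illustrate the consequence of one reading that the text leaves open and do not measure this trial's error rate. They also assume no interim looks, although the design is called sequential and adaptive. The 0.34 SD example was chosen close to the cut-off.

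**A justified margin could leave the trial underpowered.** This stands. Step 6 gives 40% power at 0.3 SD and 63% at 0.4 SD, so the stated power could fall substantially.

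**Intention to treat alone can favour similarity in a non-inferiority trial.** That is a separate matter of the analysis set, and it does not change the conclusion here.

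**Conclusion.** The concern holds and must be fixed. The document declares non-inferiority, states only a no-difference hypothesis, and gives no margin, error level, confidence-interval rule or named instrument. As written, it does not prespecify a test that could establish non-inferiority, and a margin set after outcome data are seen could not repair that. This conclusion depends on the text alone and on none of the assumed numbers.

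The figures show what is at stake: under the working assumptions, a non-significant result is compatible with deficits larger than any margin for which 65 per group would conventionally be sized. They do not show that 65 per group is wrong; that cannot be judged until the margin is stated.

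**What to change.** Before recruitment opens ("Recruitment will be aimed to start in August", in a protocol dated 10 July 2016), amend the hypothesis, sample-size and analysis text as follows.

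- **Hypothesis.** Replace the sentence with: H0: mean tinnitus distress (higher = worse) on [named instrument] post-intervention, iCBT minus standard care, ≥ margin; H1: < margin. This also labels the primary time point.
- **Margin.** State it in points of that instrument, with a clinical justification.
- **Decision rule.** Claim non-inferiority only if the upper confidence limit lies below the margin, at a stated confidence level. Say whether the sequential adaptive design includes interim efficacy looks; if it does, the level must allow for them.
- **Interpretation.** State that a non-significant difference is not evidence of non-inferiority.
- **Sample size.** Report the alpha, power and dropout assumption that 65 per group delivers for the chosen margin. If power is low, restate it or limit the claim; enlarging the trial is not needed for this repair.

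The cost is an amendment to the text, plus the work of choosing and justifying the margin. Sample size and visits do not change. The downside is that the stated power may be less favourable, possibly by a wide margin if a small difference is judged clinically important.

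### The plan says follow-up will establish that both treatments are effective, but two active arms without an untreated comparison identify only the difference between them

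*Combined protocol and SAP*

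**What the plan says.** The STUDY DESIGN section of the protocol sets out the design as follows: "A randomised, multi-centre, two-arm parallel group, non-inferiority trial with a sequential adaptive design and a two-month follow-up will be followed". Both arms are active. For the first, "The experimental group will receive eight weeks of guided internet-delivered treatment"; for the second, "The control group will receive a standard individual face-to-face audiological care". The hypothesis concerns the contrast between arms: "The hypothesis is that there will be no difference in outcomes for the treatment and control groups". The next sentence gives the purpose of follow-up: "These groups will be followed prospectively for two months, to establish the maintenance and effectiveness of both treatments on tinnitus distress".

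The OBJECTIVES section is comparative. Its lead statement is "The primary aim of this study is to evaluate the effectiveness of iCBT for tinnitus distress, compared to standard care", and the key secondary and longer-term objectives are also set against standard care.

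On who enters, the Inclusion Criteria require "Experiencing tinnitus distress deemed to require a referral to the tinnitus clinic by the referring ENT Specialist or Audiologist". They set no score threshold, minimum duration or period of stability.

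On prior evidence, the INTRODUCTION states "Initial clinical trials indicated that iCBT in the UK is effective at reducing tinnitus distress and associated comorbidities", without an effect size. It offers no corresponding statement for face-to-face care. The only statement about analysis, under Withdrawal, is that it will be by intention to treat.

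**The concern.** The follow-up sentence promises a conclusion about each treatment separately, comparator included. It cannot be read as shorthand for iCBT minus standard care. Randomisation between two active arms supports a statement about their difference and nothing more. A statement about one arm alone would have to rest on change from baseline. That change mixes any treatment effect with whatever would have happened anyway: the natural course of distress after referral, and possibly regression to the mean.

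The result the trial hopes for is the one that exposes the gap. With a hypothesis of no difference, success looks like similar improvement in the two arms. A reader holding the protocol could then report that both treatments were shown to work and that their effects lasted, citing this sentence as the pre-stated purpose. The trial's own data could not distinguish that account from one in which distress eased without help from either treatment.

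**Working it through.** **What is identified.** Write the mean change in each arm as the sum of two parts:

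- change in iCBT arm = N + E1
- change in standard-care arm = N + E2

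N is the change that would occur without treatment, and E1 and E2 are the treatment effects. Randomisation makes N equal in expectation across arms, so the between-arm difference is (N + E1) − (N + E2) = E1 − E2. This is free of N, which is why the primary comparison is sound. But there are two observed quantities and three unknowns. Equal changes imply E1 = E2 and leave their common value open, including zero. Separating N would need an untreated or waiting group, a stable pre-treatment period or an external benchmark, and the text describes none of these.

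The same holds for the period from end of treatment to two months. Stable scores over that period can be described, but they cannot be attributed to a lasting treatment effect.

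**Sample size used.** The plan gives 65 per group. The site targets agree if 50 is read as applying to each of two sites: 50 + 50 + 30 = 130 = 2 × 65. The documents do not state the inputs to the 65, so it cannot be reproduced. It is taken as given here, and the point does not depend on it.

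**Illustration of how within-arm change could mislead.** The following are assumptions, not figures from the documents: no treatment effect in either arm; a shared untreated improvement of s (in SD of the distress score, equal at both times); baseline-to-post correlation r of 0.5 to 0.7; a two-sided 5% paired test in one arm with n = 65, by normal approximation.

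- SD of change = √(2(1 − r)): 1.000 at r = 0.5 and 0.775 at r = 0.7
- λ = s√65 / √(2(1 − r)), with √65 = 8.062
- Probability of significance = 1 − Φ(1.96 − λ) + Φ(−1.96 − λ)

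| s | r | λ | Probability |
|---|---|---|---|
| 0.2 | 0.5 | 1.61 | 36% |
| 0.2 | 0.7 | 2.08 | 55% |
| 0.3 | 0.5 | 2.42 | 68% |
| 0.3 | 0.7 | 3.12 | 88% |

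The expected between-arm difference is zero in every row.

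**How much regression to the mean could contribute.** Patients are selected by a clinician's judgement at referral. The study baseline is a separate online assessment, which Table 1 lists after recruitment and consent. Suppose the referred patients are the most distressed fraction q. Let a be the correlation of referral severity with baseline and b its correlation with the post-treatment score. The expected fall is m(a − b), where m = φ(c)/q and c is the upper-q normal quantile.

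- q = 0.5: m = 0.80. With a = 0.8 and b = 0.7, the fall is 0.80 × 0.1 = 0.08 SD.
- q = 0.2: m = 1.40. With a = 0.8 and b = 0.6, the fall is 1.40 × 0.2 = 0.28 SD.
- a = b: the fall is 0.

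These values of q, a and b are also assumptions. Regression to the mean could therefore be small or absent. Natural course remains a possible source of N in either case.

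**The case against.** The strongest reply is that the plan is comparative almost everywhere else. The stated aim, every effectiveness objective and the hypothesis are between-arm, and the longer-term objective already covers most of what the follow-up sentence should say. On that view this is one loose sentence outside the OBJECTIVES section. Moreover, no within-arm test, success rule or reporting rule is specified, so the harm is inferred rather than planned. Much of this stands. It limits the point to wording and interpretation. It does not cancel the sentence, which states a purpose that the design cannot meet. Nor does the plan restrict analysis in a way that would stop the claim being made.

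A second reply is that earlier UK trials are said to support iCBT, so the possibility that neither treatment works is less open than the algebra suggests. That is fair for iCBT. But such support comes from outside this trial, is given without an effect size, and does not extend to the comparator, while the sentence covers both.

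A reader might also infer three stronger things that the documents do not support:

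- **That the randomised comparison is biased by natural course or regression to the mean.** It is not. Both are expected to be equal across arms.
- **That the plan intends to declare effectiveness from before-after tests.** It names no such test, so the percentages above are not error rates of a planned analysis.
- **That these patients are known to improve untreated, or that regression to the mean must be large because they enter at referral.** The documents name no outcome measure and say nothing about untreated course. With a separate baseline after referral, regression to the mean may be zero.

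**Conclusion.** The point holds as a mismatch between one stated purpose and the design. The conclusion about identification needs only what the text states: two active arms and no untreated comparison, stable lead-in or benchmark. It needs no numerical assumption.

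The numbers only show that the gap could matter in practice. If distress eased by 0.2 to 0.3 SD without treatment, a within-arm test with 65 patients would be significant in roughly 36% to 88% of trials in which neither treatment did anything. Those figures rest on the assumed shift and correlations, and the documents supply neither.

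The primary comparison, the sample size and trial conduct are untouched. What changes is the conclusion that may be drawn if the arms come out alike. The stated comparative aims do not require an untreated arm, and this point does not ask for one.

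**What to change.** In STUDY DESIGN, replace the follow-up sentence with: *to compare the two treatments on tinnitus distress at the end of treatment and at two months, and to compare the change between these times.*

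Add two statements:

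- Change within an arm is descriptive and will not be presented as evidence that a treatment is effective or that its effect is maintained.
- If the arms are similar, the conclusion is limited to iCBT relative to the face-to-face care given at these sites.

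If the investigators wish to keep a claim about each treatment, they would need to document outside evidence, with effect sizes, for both iCBT and standard care, and say that the claim rests on it.

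The cost is wording only, with no change to recruitment, assessments or sample size. The downside is a narrower permitted claim: the trial could not report on its own authority that either treatment works or that its effect lasts.
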